#### **1.4. Current Therapeutic Options for g-HAT**

Few therapeutic options are currently available to treat HAT at either stage (1, 14). When early-stage HAT is diagnosed, patients can be treated in their villages with intramuscular injections of pentamidine for 7 days. In patients with late-stage HAT, NECT, a combination of oral nifurtimox for 10 days plus eflornithine, two 2-hour intravenous (IV) infusions daily for 7 days, was found to provide similar cure rates to the standard regimen with eflornithine for 14 days, but with obvious practical advantages, including ease of administration and a shorter duration of treatment.

In May 2009, the WHO Expert Committee added NECT to the 16th edition of the WHO List of Essential Medicines for adults, as an alternative to single-drug therapy with melarsoprol or eflornithine.

In keeping with the WHO recommendation, almost all of the national HAT control programmes have already adopted NECT as first-line treatment for late-stage g-HAT and, in 2014, NECT became the most widely used treatment for late-stage disease (21).

NECT represents a significant improvement over current therapies, however it is far from ideal given the conditions under which patients with HAT generally live, i.e. in poor, remote areas with little or no healthcare infrastructures and problems with logistics. Thus, there is an urgent need to develop easier-to-use products for the treatment of this fatal disease, ideally a simplified, short-course treatment that can be administered orally at a primary healthcare facility or indeed on an out-patient basis.

#### **1.5. Investigational Product and Preclinical Data**

Acoziborole (SCYX-7158) is an orally active benzoxaborole-6-carboxamide. Acoziborole, also referred to as [REDACTED], is the result of a collaboration between DNDi, [REDACTED]

[REDACTED]. Preclinical studies have identified the concentrations of acoziborole that must be achieved in the plasma and brain in order to be effective against late-stage g-HAT. Indeed, reversible *in vitro* assays for acoziborole showed that it is necessary to know the exposure time and area under the curve (AUC) for the minimum inhibitory concentration in order to predict efficacy.

Complete and irreversible inhibition of parasite growth was achieved with an unbound AUC of 5.81  $\mu\text{g}\cdot\text{h}/\text{mL}$ . This was confirmed in animal models considered to be predictive of HAT in humans in which a 100% trypanocidal effect was obtained with daily administration of 25 mg/kg for 7 days. On the first day of

treatment, plasma concentrations reached 4.98  $\mu\text{g}\cdot\text{h}/\text{mL}$ , which is close to the critical threshold of 5.81  $\mu\text{g}\cdot\text{h}/\text{mL}$  for the unbound AUC of the minimum inhibitory concentration. From the second to the seventh day, the threshold was exceeded, and concentrations reached 7.15  $\mu\text{g}\cdot\text{h}/\text{mL}$  (28).

Preclinical pharmacokinetic (PK) studies showed that acoziborole is well absorbed by the oral route, that it is widely distributed throughout the body and that it crosses the blood-brain barrier. In all of the animal species studied, acoziborole was rapidly metabolised through oxidation, leading to the formation of at least one inactive metabolite, SCYX-3109 (10). Toxicological studies, including safety pharmacology and 4-week repeated-dose toxicity studies (including toxicokinetics) in the rat and dog, have shown that acoziborole is well tolerated up to 40 mg/kg/day in rats, with no major toxicities identified. In both species, 15 mg/kg/day was considered as the no observed adverse effect level in the 4-week repeated-dose studies.

### **1.6. Pharmacokinetics and Metabolism In Healthy Volunteers**

A randomised, double-blind, placebo-controlled Phase-I study (6) was performed in healthy African male volunteers between 18 and 45 years of age in order to assess the safety, PK and pharmacodynamics (PD) of acoziborole after single ascending oral doses. A total of 128 subjects were included, 102 of whom received acoziborole, and 26 received placebo. The doses studied ranged from 20 mg to 1200 mg.

Acoziborole was rapidly absorbed in the healthy volunteers, and the plasma concentrations remained stable for at least 96 hours, indicating that the elimination half-life is relatively long. Analysis of the PK data showed that acoziborole undergoes extensive enterohepatic recycling. Activated charcoal was administered to subjects, generally starting on Day 5, in order to accelerate clearance of the product and shorten the follow-up period for the subjects. The therapeutic dose of 960 mg was also administered without activated charcoal to mimic the future conditions of administration to patients. Clearance of acoziborole from the body was very slow with a half-life of approximately 400 hours. This profile suggests that a single administration of acoziborole may be sufficient for the treatment of HAT. Inter-subject variability was low at approximately 20%.

Contrary to what was observed in animals, metabolism of acoziborole was very limited, which may explain the very long half-life in humans.

The unbound fraction was determined by ultrafiltration. The ultrafiltrate-to-plasma ratio was in the same range as that in the *in-vitro* study. The mean unbound fraction was 2.2% of the plasma concentration.

In addition, concentrations of acoziborole were determined in the CSF of healthy volunteers. In the 240 and 320 mg dose-level groups, mean CSF concentrations corresponded to 2.2% of the plasma concentration with a range of 1.8% to 3.2%.

## 1.7. Safety in Healthy Volunteers

The safety of acoziborole was assessed in the Phase-I study (6).

The most frequently reported acoziborole-related adverse events (AEs) were gastrointestinal disorders, mainly consisting in abdominal pain, nausea, constipation, vomiting and, more rarely, reduced appetite. The AEs were observed at different doses of acoziborole and were also observed with placebo. It should be noted that the use of activated charcoal promoted the occurrence of some gastrointestinal disorders such as constipation or vomiting. Central nervous system disorders were also reported, mainly consisting in headache, but none were considered to be possibly related to acoziborole. No correlation was found between the dose and the number of AEs observed.

No relevant abnormal findings were observed on clinical monitoring, i.e. physical examination, vital signs and electrocardiograms (ECG). Conversely, laboratory monitoring found a few clinically significant abnormalities with acoziborole, as well as with placebo, primarily consisting in elevated levels of creatine phosphokinase and of transaminases. In addition, thyroid function tests found irregular and incomplete, sub-clinical variations in TSH, free T3 and free T4, in the acoziborole group, as well as with placebo. One case of sub-clinical hyperthyroidism after administration of acoziborole at 240 mg was however reported as a serious adverse event (SAE). The case was mild in severity, sub-clinical, transient and spontaneously resolute, and was considered to be possibly related to acoziborole. The variations were observed in both the placebo and the acoziborole groups, regardless of the dose, however considerably fewer variations were observed in the higher dose-level groups, including the selected therapeutic dose.

In subjects exposed to acoziborole, no abnormalities were observed in the following parameters: bilirubin, pancreatic function (blood glucose, lipase and amylase) lipid profile (triglycerides, total cholesterol, high-density lipoproteins - cholesterol, low-density lipoproteins - cholesterol), kidney function (creatinine, urea, electrolytes), haematology, coagulation tests (activated partial thromboplastin time, international normalised ratio), reticulocytes, haptoglobin, ferritin and Coombs test.

## 1.8. Choice of the Dose and Dosing Regimen

The dose of 960 mg was chosen as the therapeutic dose because it ensures exposure levels in the CSF 1.5-fold higher than the pharmacologically active levels at which a 100% trypanocidal effect was obtained in infected animals. In healthy volunteers, plasma levels remained above the effective concentration up to 69 days after the administration of acoziborole.

No safety signals were observed at 1200 mg, which was the highest dose tested in humans. This provides a safety margin approximately 1.5- to 3-fold higher than the no observed adverse effect level in animals.

No studies have been performed on the effect of food on the bioavailability of acoziborole and, for this reason, the single dose of the investigational product must be taken in the fasting state.

### **1.9. Rationale for the Study Design**

The principle of an open-label, non-randomised, prospective study was accepted by the European Medicines Agency, taking into account the difficulty of completing enrolment of late-stage HAT patients in a prospective, randomised, non-inferiority study within a reasonable timeframe.

The European Agency recommended calculating the sample size in the present non-randomised study based on the maximum feasible enrolment within a reasonable timeframe.

Given the drastic decline in prevalence, it was estimated that the sample size that is possibly feasible to attain within a reasonable timeframe, i.e. approximately 28 months, is 155 patients with late-stage g-HAT, with a provision of 5% (7 patients) to allow for possible replacement of patients lost to follow-up who fled the region due to armed conflict or natural disaster, for a total of 162 late-stage patients.

### **1.10. Target Population**

The target population will initially be limited to patients 15 years of age or older with late-stage HAT. After the first futility analysis, a second cohort of patients with early- or intermediate-stage HAT will be enrolled in order to enrich the safety database on acoziborole and to assess its efficacy in this population.

As in the preceding studies on HAT, the inclusion of adolescent patients 15 years of age or older, in addition to adults, will facilitate the enrolment of patients with late-stage HAT.

## **2. Study Objectives and Endpoints**

### **2.1. Objectives**

#### **2.1.1. General Objective**

The aim of the study is to assess the efficacy and safety of a single oral dose of acoziborole administered to patients in the fasting state with g-HAT.

### **2.1.2. Primary Objective**

The primary objective is to estimate the success rate at 18 months of follow-up with acoziborole, administered as a single 960-mg oral dose to patients in the fasting state with late-stage g-HAT.

An estimate of the success rate observed with NECT in patients with late-stage g-HAT, based on historical data, will be provided as a yardstick.

### **2.1.3. Secondary Objectives**

- To estimate the success rate at 12 months in late-stage patients
- To estimate the time course of the failure rate in patients with late-stage g-HAT.
- To assess the safety profile of a single dose of acoziborole in patients with g-HAT using historical data on NECT as a yardstick.
- To establish the relationship between, on the one hand, concentrations of acoziborole in the blood and the CSF and, on the other hand, the efficacy and safety of acoziborole.

A cohort of patients 15 years of age or older with early- or intermediate-stage g-HAT will be enrolled following the futility analysis, provided that the latter does not show futility and that the safety review shows no concerns. The overall objective will be to assess the efficacy of acoziborole in this cohort and to enrich the safety database at the time of regulatory filing.

- To estimate the success rate with acoziborole in this cohort, using pentamidine as a yardstick, in order to verify the underlying hypothesis according to which, in HAT, a treatment able to clear the parasite from the CSF also clears it from the other compartments.
- To assess the safety profile in this cohort and in the overall population.
- To assess the safety of acoziborole in patients with early- and intermediate-stage HAT to determine whether its safety profile is comparable to the historical safety profile of pentamidine.

## **2.2. Endpoints**

### **2.2.1. Primary Endpoint – Efficacy**

#### **Primary Endpoint for Patients with Late-stage HAT**

A patient will be considered as a success, in accordance with the WHO criteria (23), if the patient is alive with no evidence of trypanosomes in any body fluid and a CSF WBC equal to or below 20/ $\mu$ l 18 months after receiving acoziborole.

A patient with no parasitological evidence of a relapse and a CSF WBC above 20/ $\mu$ L or who, in the Investigator's opinion, requires rescue treatment will be considered as a probable relapse.

A patient who refuses the end-of-study lumbar puncture will be classified as a probable cure (success) in the absence of any clinical signs or symptoms suggestive of THA or with another obvious aetiology, provided that the outcome was favourable, i.e. a CSF WBC equal to or below 20/ $\mu$ l, at the last available assessment at 6 months or later.

Death for any reason, patients lost to follow-up and not retrieved or patients who refuse a lumbar puncture at 18 months and who had an unfavourable outcome earlier (probable relapse) will be considered as failures, with the exception of patients who fled the region due to armed conflict or natural disaster. These patients will be replaced by patients from another centre in order to maintain the planned sample size. In order to allow for replacement of some patients lost to follow-up due to armed conflict and to maintain the planned sample size of 155 evaluable patients, 7 additional patients will be enrolled in the study.

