Statistical Analyses	
Analysis Sets
 
The population of late-stage patients will be separated from the population of early- and intermediate-stage patients.
 
The primary analysis will be performed on late-stage patients in the modified intention-to-treat (mITT) population and who received at least one tablet of acoziborole. Patients lost to follow-up who fled the region due to armed conflict or natural disaster will not be included in the mITT population and will be replaced by other patients.
 
The analysis of the primary endpoint for early- and intermediate-stage patients, which is considered to be a secondary analysis, will be also performed on the mITT population.
 
The sensitivity analyses will be performed by cohort, separating late-stage patients from early- and intermediate-

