##### **Endpoints in Patients with Early- or Intermediate-stage HAT**

Two efficacy endpoints will be used for patients with early- and intermediate-stage HAT: the outcome at 12 months and the outcome at 18 months after receiving treatment. A patient will be considered as a success at 12 months if the patient is alive with no evidence of trypanosomes in any body fluid and if the CSF

WBC is equal to or less than 20/ $\mu$ L. A patient with no parasitological evidence of relapse, but with a CSF WBC above 20/ $\mu$ L or who, in the Investigator's opinion, requires rescue treatment, will be considered as a relapse. A patient who refuses the lumbar puncture at 12 months will be classified as a probable cure (success) in the absence of any clinical signs or symptoms suggestive of THA or with another obvious aetiology, provided that the outcome was favourable, i.e. a CSF WBC equal to or less than 5/ $\mu$ L, at 6 months. Death for any reason, patients lost to follow-up and not retrieved or patients with no post-treatment lumbar puncture will be considered as failures, with the exception of patients who fled the region due to armed conflict or natural disaster. For memory, patients who fled the region due to armed conflict or natural disaster will not be included in the mITT population and will therefore not be taken into account in the calculation of the success rate. A patient with early- or intermediate-stage HAT will be considered as a **success** at 18 months if the CSF WBC is equal to or below 20/ $\mu$ L and in the absence of trypanosomes, rescue treatment and signs or symptoms suggestive of a relapse. If the patient does not have a lumbar puncture at 18 months, the outcome at 6 months or at 12 months will be used.

A patient with early- or intermediate-stage HAT will be considered as a success at 6 months and at 12 months if the CSF WBC is equal to or less than 20/ $\mu$ L and in the absence of trypanosomes, rescue treatment and signs or symptoms suggestive of a relapse. If the patient does not have a lumbar puncture at 6 months, the outcome at 12 months and, if necessary, at 18 months will be used. If the patient does not have a lumbar puncture at 12 months, the outcome at 18 months will be used and, if necessary, the outcome at 6 months will be used. If no post-treatment lumbar punctures were performed, the outcome will be considered as unfavourable.

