**Table 5 - Populations Used in the Analyses**

Type	Aim	Definition
Primary: modified intent-to-treat (mITT) patients	Primary analysis	All patients who received at least one tablet of acoziborole, excluding patients who fled the region due to armed conflict or natural disaster, or due to force majeure, and for whom no post-treatment data are available. These patients will be included in the population as failures for an “all-patient” sensitivity analysis.
All patients	Safety analyses and sensitivity analyses on efficacy	All patients who received at least one tablet of acoziborole. There will be no exceptions to this rule.
Secondary: evaluable patients	Sensitivity analyses on efficacy	Patients in the mITT population for whom at least one lumbar puncture is available (at 6, 12 or 18 months), and excluding patients who died for reasons clearly unrelated to efficacy or safety, or who fled the region due to armed conflict or natural disaster.
Secondary: per-protocol patients	Sensitivity analyses on efficacy	Patients in the mITT population with no major protocol violations. Major violations will be described by patient, and exclusion will be decided during the data review.

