## 9.8. Handling of Missing Data and Patients Lost to Follow-up

The primary endpoint is the outcome at 18 months. If outcome assessed at the final visit is missing, the **primary imputation method** will consist in imputing a probable success (considered as a success) to patients who attended the 18-month visit, but who refused the lumbar puncture planned at the visit, who showed no signs or symptoms of HAT at 18 months, who did not subsequently report any symptoms of relapse and for whom the outcome was considered as favourable at the last available assessment (17). If these criteria are not fulfilled, the patients will be considered as treatment failures. The outcome for patients who did not attend the 18-month visit or later will also be considered as a failure, except for patients who fled the region due to armed conflict or natural disaster.

Because the historical data may not allow for other imputation methods to be applied, only the primary imputation method will be used. The method will be described in detail in the SAP. Sensitivity analyses will be performed to assess the impact of missing data on acoziborole. The method will be described in detail in the SAP.

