## 5. ANALYSIS SETS AND SUBGROUPS

The analysis sets are defined below:

- **Set of screened HAT positive patients:** All HAT positive patients who signed the informed consent. To be noted that after the 1st DSMB meeting, recruitment of stage 1 and intermediate stage HAT patients was authorized. That will trigger a modification of the initial screened set.
- **Treated set:** all patients who received at least one tablet of acoziborole.
- **Modified Intention-To-Treat (mITT):** All patients who received at least one tablet of acoziborole, excluding patients (\*) who fled the region due to armed conflict or natural disaster or due to force majeure (\*\*) and for whom no failure was detected early (parasite, needs for rescue medication, death or more than 50 WBC/µL in CSF at M6) and no data are available at M12 and M18 due to armed conflict, natural disaster or force majeure affecting the site.
- **Evaluable patients:** Modified Intent-to-treat patients (mITT) and excluding:
  - Patients lost to follow-up at 18 months (for primary efficacy endpoint and secondary efficacy outcome at 18 month), patients lost to follow-up at 12 months (for secondary efficacy outcome at 12 month), patients lost to follow-up at 6 months (for secondary efficacy outcome at 6 month), except those who were a failure before being lost to follow-up (cf. [Section 7.7](#) for programming rules).
  - Patients with no post-treatment lumbar puncture (i.e. patients who refused all lumbar puncture after treatment and who were not a failure)
  - Patients who died for reasons clearly unrelated to efficacy or safety or disease evolution (\*\*).
  - Early consent withdrawal (before M6, i.e. no planned visit attended after 3-month visit).
- **Per Protocol Set (PPS):** Modified Intent-to-treat patients (mITT) with no major protocol deviations (\*\*\*). Major deviations will be described by patient, and exclusion will be decided during the data review (cf. [Section 8.2](#)).

Notes:

(\*) These patients will be included in the Treated set population as failures.

(\*\*) This will be reviewed during data review meeting (e.g. review of comments and reasons of early discontinuation in end-of-study form).

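### Losses put down to undefined force majeure are primary failures under the protocol's endpoint and missing-data rules, but leave the primary denominator under Protocol Table 5 and the SAP mITT definition

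*Protocol*

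**What the plan says.** **Two causes.** Protocol 2.2.1 treats a patient lost and not retrieved as a failure, "with the exception of patients who fled the region due to armed conflict or natural disaster". Section 9.8 says the same of patients who miss the 18-month visit: they "will also be considered as a failure, except for patients who fled the region due to armed conflict or natural disaster". The Protocol Summary, repeated in the 9.2 body text, states the analysis-set version: "Patients lost to follow-up who fled the region due to armed conflict or natural disaster will not be included in the mITT population". Section 2.2.2 repeats it for the early/intermediate cohort: "patients who fled the region due to armed conflict or natural disaster will not be included in the mITT population". The replacement rules (Protocol 2.2.1, 8.1 and 9.1; SAP 5) also name only conflict or disaster.

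**Three causes.** Protocol Table 5 defines mITT by excluding patients who fled for those two reasons "or due to force majeure, and for whom no post-treatment data are available". SAP 5 excludes patients "who fled the region due to armed conflict or natural disaster or due to force majeure", provided that no early failure was detected and that M12 and M18 data are missing because of such an event. SAP 8.1 uses the same three causes in the disposition table. Neither document defines force majeure. The SAP 5 note attached to it reads: "This will be reviewed during data review meeting".

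Protocol 9.6.1 and SAP 8.6.1.1 both run the primary analysis on mITT.

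**The concern.** Two stated rules give different primary estimates for the same patient. The rules for study success (Protocol 9.6.2, SAP 8.7) set no formal criterion: the estimate and its lower confidence limit are read against historical NECT results. Who is in the denominator therefore bears directly on the conclusion.

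The third cause is open-ended. It is assigned at data review from comments and end-of-study reasons, in an open-label trial, when it is already known that the patient will count as a failure unless excused. Each such exclusion removes one failure and leaves the number of successes unchanged, so the effect has one direction. The replacement rules do not cover force majeure, so a patient excluded for it would also shrink the primary set below plan.

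**Working it through.** **1. The same patient under each rule.** Take a treated late-stage patient with no detected early failure, recorded as lost for a reason called force majeure, with no post-treatment data.

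| Source | Causes excused | Status of this patient |
|---|---|---|
| Protocol 2.2.1, 9.8 | conflict, disaster | failure |
| Protocol Summary, 9.2 text | conflict, disaster | stays in mITT, so counted as a failure |
| Protocol Table 5 | conflict, disaster, force majeure | outside mITT |
| SAP 5 (mITT) | conflict, disaster, force majeure | outside mITT |
| SAP 6.1, 10.1 (box 4) | none; every loss fails | failure if in the set analysed |
| Replacement rules | conflict, disaster | not replaced |

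The SAP is coherent with itself here. Its endpoint fails every loss, and 7.6.2 says that intercurrent events are handled partly through the population definitions. The contradiction lies within the protocol, between Table 5 on one side and 2.2.1, the 9.2 text and 9.8 on the other. The SAP follows Table 5.

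**2. Reproducing the plan's figures.** The Jeffreys interval is the 2.5% and 97.5% quantiles of Beta(x + 0.5, n − x + 0.5). Protocol 9.1 gives 83.4–93.2 for 89% and 89.7–97.1 for 94% with 155 patients. With whole patients, 138/155 gives 83.4–93.2 and 146/155 gives 89.7–97.1. Both match.

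**3. Size.** The number of force-majeure losses, k, is not in the documents and is an assumption. Start from 155 treated late-stage patients and 9 failures, k of which are such losses. Counted as failures, the rate is 146/155. Excluded, it is 146/(155 − k).

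| k excluded | Rate | 95% Jeffreys | Change in rate | Change in lower bound |
|---|---|---|---|---|
| 0 | 146/155 = 94.2% | 89.7–97.1 | – | – |
| 1 | 146/154 = 94.8% | 90.4–97.5 | +0.6 | +0.8 |
| 3 | 146/152 = 96.1% | 92.0–98.3 | +1.9 | +2.4 |
| 5 | 146/150 = 97.3% | 93.8–99.1 | +3.1 | +4.1 |

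(Changes are taken before rounding.)

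Setting the losses on top of 9 other failures gives nearly the same gap. With k = 3, it is 143/155 = 92.3% (87.3–95.7) against 143/152 = 94.1% (89.5–97.0), a difference of 1.8 points in the rate and 2.2 in the lower bound.

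**4. Context.** SAP Table 4 gives a pooled NECT rate of 354/376 = 94.1% (91.4–96.2). In this example, three exclusions move the acoziborole lower bound from below 91.4 to above it. That limit is not a decision threshold, but it is the kind of comparison a reader will make. The same table shows what removing three patients does to the NECT arm of the fexinidazole study: 124/130 = 95.4% becomes 124/127 = 97.6%. Those three fled armed conflict, a cause that every section excuses, so this illustrates the arithmetic only.

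**The case against.** The best reply is that the primary set is not really in doubt. Both documents assign the primary analysis to mITT, both formal definitions of that set include force majeure, and the 9.2 text refers the reader to Table 5. The alternative result is also visible: excluded patients count as failures in the Treated-set analysis (SAP sensitivity analysis #3), and listing 16.2.3 shows who was left out of mITT. There is also a fair argument that losses caused by outside events should not be charged to the drug.

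Much of this stands, and it limits the seriousness of the point. But the 9.2 text and the Protocol Summary state the mITT exclusion with two causes, and 9.8 counts every other loss as a failure. A sensitivity analysis shows the size of the difference without saying which rule governs the primary estimate.

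Three stronger readings may tempt a reader, and the documents do not support them:

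- *That the SAP added the cause without declaring it.* SAP 11 lists departures from the protocol. On the cause of exclusion the SAP repeats Table 5, so there was nothing to list.
- *That known failures could be relabelled.* SAP 5 bars exclusion of anyone with a parasite found, a need for rescue medication, death, or more than 50 WBC/µL in CSF at M6, and requires that M12 and M18 data be absent. What is known at data review is the default failure status, not an 18-month result.
- *That the SAP's reference to events at the site widens the category.* It sits in an additional condition on the missing M12 and M18 data, so it narrows the exclusion.

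**Conclusion.** The point holds as an inconsistency inside the protocol that is carried into the SAP: two causes in the endpoint, missing-data and body text, three in Table 5, SAP 5 and SAP 8.1, with the third undefined and judged at data review. It affects only losses that would fail by default and that meet the data conditions. For those, exclusion can only raise the primary rate.

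Under the assumed 146/155, the effect is about 0.6 points for one patient, 1.9 for three and 3.1 for five, with the lower bound rising by 0.8, 2.4 and 4.1 points. These counts are illustrations. Nothing in the documents shows that any such loss occurred or was expected, and the whole provision for conflict and disaster losses is 7 patients. With no such losses the effect is nil. No figure stated in the plan is wrong. It should be corrected because the estimate and lower bound carry the whole interpretation, but it does not undermine the design.

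**What to change.** Use one list of excused causes in the Protocol Summary, Protocol 2.2.1, 2.2.2, the 9.2 text, Table 5 and 9.8, and in SAP 5 and 8.1. Either of two routes resolves it:

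1. Delete force majeure from Table 5, from both places in the SAP 5 mITT definition and from SAP 8.1. Such losses then count as failures in the primary analysis, and their exclusion is reported only as an added sensitivity analysis.
2. Keep it as a closed list of dated, site-level events, fixed before data review by people without sight of patients' outcome status. Add it to the endpoint and missing-data sections and state whether these patients are replaced.

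The data condition should be aligned in the same edit, because Table 5, SAP 5 and SAP 8.1 each word it differently.

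The cost is wording, plus one extra table under the first route. The primary rate may come out slightly less favourable.
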